7.1.1 Screening

Prior to commencement of the screening examination, the patient must have given full informed consent and have completed the study Informed Consent form. Once this has been signed and dated by the patient or the patient's legal representative, then the investigator can undertake the required assessments to confirm the patient's eligibility for the study.

Ocular and Audiometry examinations must be performed at screening. In the case that the examination(s) had already been performed 6 months prior to screening, then the examination(s) do not need to be repeated. The examination(s) can be performed at any time at the investigators discretion if symptomatically/clinically indicated.

Serum ferritin, serum creatinine and proteinuria (urine protein/ creatinine ratio) will be measured during the screening visit for eligibility criteria.

The serum ferritin samples should be obtained in the absence of known infection.

Pregnancy test will be required only for females with child bearing potential.

The full list of assessments to be performed during the screening period (including the 5-day wash out period for patients previously treated with deferiprone (DFP) or deferoxamine (DFO)) is detailed in [Table 7-1](#).

See [Section 7.1.1.2](#) to get information on how to process screen failures.

Patients that do not meet the eligibility criteria are not allowed to be re-screened.

7.1.1.1 Eligibility screening

Following registration for screening, patient eligibility will be checked once all screening procedures are completed, and before study drug is provided to the patient.

7.1.1.2 Information to be collected on screening failures

Patients who sign an informed consent but fail to be started on treatment for any reason will be considered a screen failure. The reason for not being started on treatment will be entered on the Screening Log.

The demographic information, informed consent, inclusion/exclusion evaluation and Screening log pages in the eCRF must also be completed for Screen Failure patients. No other data will be entered into the clinical database for patients who are screen failures, unless the patient experienced a Serious Adverse Event (SAE) during the Screening Phase (see [Section 8](#) for SAE reporting details).

7.1.1.3 Patient demographics and other baseline characteristics

Data will be collected on patient characteristics including demographic information (age, sex, ethnicity, etc.) and other background or relevant medical history/ current medical condition, transfusion history, disease history, prior chelation history, serum pregnancy test, vital signs at Screening visit.

To determine eligibility to be enrolled into the study, patients will also undergo assessments as per the inclusion and exclusion criteria which include hematology and biochemistry evaluations, hepatitis viral evaluation, serum ferritin, serum creatinine and creatinine clearance, a known history of HIV positive test result (ELISA or Western blot) which is documented in the source documents, active Hepatitis B and/or C, serum pregnancy test and urinalysis.

Other assessments include chest x-ray (if clinically indicated), ocular exam, audiometry and ECG.

Specifics are given on [Table 7-1](#) and [Table 7-2](#). Patients who meet all the inclusion/exclusion criteria at screening will be admitted for baseline evaluations. All baseline results for safety evaluations must be available prior to dosing on Day 1.

At baseline visit (day 1), a verification of eligibility will be performed prior to performing any baseline assessments and administering the study drug.

7.1.2 Treatment period

The duration of core phase treatment is 48 weeks. Patient visits will occur every 2 weeks during the first month of treatment and then every 4 weeks thereafter until Visit 777 (SEC).

Having completed the screening period (including the 5-day wash out period for patients previously treated with deferiprone (DFO) or deferoxamine (DFP)), patients who are eligible will be enrolled to receive deferasirox DT during 24 weeks then switch to deferasirox FCT for 24 weeks. Daily dose is calculated by the physician based on the patient's actual body weight.

At the start of treatment, iron chelation naïve patients will receive deferasirox DT 10 mg/kg (NTDT patients) or 20 mg/kg (TDT patients) once daily then will transition to the equivalent FCT dose as outlined in the following table.

Table 7-3 Equivalent dose to be used: Deferasirox DT vs Deferasirox FCT

Equivalent dose to be used	
Deferasirox DT (mg/kg/day)	Deferasirox FCT (mg/kg/day)
5	3.5
10	7
15	10.5
20	14
25	17.5
30	21
35	24.5
40	28

All iron chelation pre-treated patients will follow the below guidance:

Patients who were taking deferoxamine (DFO), will need to take the deferasirox DT equivalent deferasirox. For deferiprone (DFP) the dose of deferasirox DT will be based on their serum ferritin. Please refer to [Table 6-2](#).

At the Week 48 visit, patients will roll over to the extension phase in the case that none of the End of Study criteria is met at that time. The patient will receive deferasirox FCT following the same dose regulations and adjustments as per the core phase.

The treatment period of the extension study is approximately 52 weeks (including treatment period (48 weeks), Study Evaluation Completion and 4 weeks Safety Follow-up visits)

For details on study design and dose adjustments, see [Section 4](#) and [Section 6.3](#).

For details of assessments, see [Table 7-1](#) and [Table 7-2](#).

7.1.3 Study Evaluation Completion visit including premature withdrawal

At the time patients discontinue study treatment; a visit should be scheduled at which time all of the assessments listed for the Study Evaluation Completion (SEC) visit will be performed. A Study Evaluation Completion eCRF page should be completed, giving the date and reason for stopping the study treatment, within 7 days following the last dose of study treatment.

At a minimum, all patients who discontinue study treatment, including those who refuse to return for a final visit, will be contacted for safety evaluations 30 days after the last dose of study treatment.

Patients who discontinue study treatment should be considered withdrawn from the study after the SEC visit assessments are performed or when it is clear that the patient will not return for these assessments.

If a study withdrawal occurs, or if the patient fails to return for visits, the investigator must determine the primary reason for a patient's premature withdrawal from the study and record this information on the Study Evaluation Completion eCRF page.

Patients who complete the extension phase will have to complete the SEC after receiving 96 weeks of treatment. The Study Evaluation Completion (777) and W96 visit will occur on the same visit and same date.

For criteria for premature withdrawal refer to [Section 7.1.3.1](#). For criteria on End of Study refer to [Section 4.3](#).

7.1.3.1 Criteria for premature patient withdrawal

Patients may voluntarily withdraw from the study or be dropped from it at the discretion of the investigator/Sponsor at any time. Patients may be withdrawn from the study if any of the following occur unless the investigator decides in the best interest of the patient to switch from deferasirox DT to deferasirox FCT:

- Pregnancy (not applicable for the switch)
- Unwillingness to comply with procedures as outlined in the study protocol, including unwillingness to comply with the prescribed study treatment
- Discovery of patient ineligibility (not applicable for the switch)
- Intake of prohibited medications (not applicable for the switch)
- Adverse event(s)
- Abnormal lab value(s)

- Unsatisfactory therapeutic effect
- Protocol violation (not applicable for the switch)
- Subject withdrew consent (not applicable for the switch)
- Lost to follow-up (not applicable for the switch)
- Administrative problems (not applicable for the switch)
- Death (not applicable for the switch)
- Decision of the Sponsor
- Unacceptable toxicity in the opinion of the investigator/Sponsor

If such withdrawal occurs, or if the patient fails to return for visits, the investigator must determine the primary reason for a patient's premature withdrawal from the study and record this information on the Study Evaluation Completion eCRF.

7.1.3.2 Withdrawal of informed consent section

Subjects may voluntarily withdraw consent to participate in the study for any reason at any time. Withdrawal of consent occurs only when a subject:

- Does not want to participate in the study anymore, and
- Does not allow further collection of personal data

In this situation, the investigator should make a reasonable effort (e.g. telephone, e-mail, letter) to understand the primary reason for the subject's decision to withdraw his/her consent and record this information.

Study treatment must be discontinued and no further assessments conducted, and the data that would have been collected at subsequent visits will be considered missing.

Further attempts to contact the subject are not allowed unless safety findings require communicating or follow-up.

All efforts should be made to complete the assessments prior to study withdrawal. A final evaluation at the time of the subject's study withdrawal should be made as detailed in the assessment table.

Novartis (sponsor) will continue to keep and use collected study information (including any data resulting from the analysis of a subject's samples until their time of withdrawal) according to applicable law.

All biological samples not yet analyzed at the time of withdrawal will no longer be used, unless permitted by applicable law. They will be stored according to applicable legal requirements.

7.1.4 Follow up period

All patients must have a safety evaluation 30 days after the last dose of study treatment (regardless if that situation occurs during core or extension phase).

For patients who are lost to follow-up, the investigator should show "due diligence" by documenting in the source documents steps taken to contact the patient, e.g., dates of telephone calls, registered letters, etc.

7.2 Assessment types

7.2.1 Efficacy assessments

Serum ferritin testing will be performed in both phases every month. The baseline serum ferritin value will be defined during the screening period.

7.2.2 Safety and tolerability assessments

Safety will be monitored by assessing physical examination, vital signs, height and weight, ECG, Chest X-ray, Ocular and Auditory examinations, laboratory evaluations as well as collecting of the adverse events at every visit. For details on AE collection and reporting, refer to [Section 8](#) (in the core and extension phase).

7.2.2.1 Physical examination

A physical examination will be performed at all study visits (refer to [Table 7-1](#) and [Table 7-2](#)). The physical examination on Day 1, will serve as the Baseline physical examination for the entire study. The exam will entail an examination of general appearance, skin, neck (including thyroid), eyes, ears, nose, throat, lungs, heart, abdomen, back, lymph nodes, extremities and nervous system.

Information about the physical examination must be present in the source documentation at the study site.

Significant findings that were present prior to the signing of informed consent must be included in the Medical History page on the patient's eCRF. Significant new findings that begin or worsen after informed consent must be recorded on the Adverse Event page of the patient's eCRF.

7.2.2.2 Vital signs

Vital signs include blood pressure and pulse measurements and will be measured at all study visits (including SEC). After the patient has been sitting for five minutes, with back supported and both feet placed on the floor, systolic and diastolic blood pressure will be measured three times using an automated validated device, e.g. OMRON, with an appropriately sized cuff. The repeat sitting measurements will be made at 1 - 2 minute intervals and the mean of the three measurements will be used. In case the cuff sizes available are not large enough for the patient's arm circumference, a sphygmomanometer with an appropriately sized cuff may be used.

Young children may be placed on their parent's / caregivers' lap for the measurement of the vital signs.

7.2.2.3 Height and weight

Height in centimeters (cm) and body weight (to the nearest 0.1 kilogram (kg) in indoor clothing, but without shoes will be measured. For specifications refer to [Table 7-1](#) and [Table 7-2](#).

7.2.2.4 Chest x-ray section

Chest x-ray will be performed at screening visit (if clinically indicated). If any chest x-ray has been performed 3 months prior to study entry the last available result will be collected.

7.2.2.5 Auditory and ocular examination

Patients will undergo auditory and ocular examinations at screening, Week 48 and at unscheduled visits (if needed). For specifications refer to [Table 7-1](#) and [Table 7-2](#)

The auditory examination includes the following assessments:

- Comprehensive audiometry threshold examination
- Speech recognition

The ophthalmologic examination includes the following assessments:

- Visual acuity test
- Tonometry
- Slit lamp exam of anterior segment
- Slit lamp exam of the lens
- Funduscopy and retinal examination

Information about the audiometry and ocular examinations must be present in the source documentation at study site. Significant findings of the audiometry and ocular examinations that meet the definition of an AE must be recorded in the adverse event summary page of the case report form.

Please follow the guidance below for children aged 2 to 5. It can also be applied for children aged 5 to 7 who cannot complete the aforementioned ocular tests:

- Sedation is not requested nor required.
- The ophthalmologist of each site must decide what is age-appropriate ocular testing without the use of sedation. If any aspect of the ocular testing listed above cannot be completed, please document this in the CRF (which assessments and the reason).
- Once the site has determined which assessment can be performed for a given patient in the screening visit, then these assessments must be repeated consistently at subsequent visits
- It is critical to collect the visual acuity results. Please collect 'best corrected' visual acuity for all patients (for example: do with glasses if done with glasses before).
- The preferred method of collection for tonometry is applanation tonometry. If not possible, then do an age-appropriate procure (without sedation).

For children aged 2 to 5 and older who do not cooperate, speech audiometry should be performed. If not possible, then the speech recognition test will be suffice.

7.2.2.6 Laboratory evaluations

All analyses will be performed by the local lab. Please refer to [Table 7-4](#) for detailed laboratory parameters.

Table 7-4 Central Clinical laboratory parameters collection plan

Test Category	Test Name
Hematology	Hematocrit, Hemoglobin, MCH, MCHC, MCV, Platelets, Red blood cells, White blood cells (WBC) count with differential (Basophils, Eosinophils, Lymphocytes, Monocytes, Neutrophils), RBC Morphology
Biochemistry	Albumin, Alkaline phosphatase, ALT (SGPT), AST (SGOT), Bicarbonate, Calcium, Chloride, Creatinine, Creatine kinase, glucose, inorganic phosphorus, potassium; sodium Direct Bilirubin, Indirect Bilirubin, Total Bilirubin, Total Cholesterol, LDL, HDL, Lactate dehydrogenase (LDH), Total Protein, Triglycerides, Blood Urea Nitrogen (BUN) or Urea, Uric Acid, C-reactive protein (CRP)
Urinalysis	Microscopic Panel (Red Blood Cells, White Blood Cells, Casts, Crystals, Bacteria, Epithelial cells) Macroscopic Panel (Dipstick) (Bilirubin, Blood, Glucose, Ketones, Leukocytes esterase, Nitrite, pH, Protein, Specific Gravity, Urobilinogen)
Hepatitis markers	HbsAg, HbsAb, HCV Ab, HCV RNA, PCR (quantitative)
Additional tests	Serum ferritin, creatinine clearance, urine protein/creatinine ratio, serum pregnancy test, urine pregnancy test

7.2.2.6.1 Hematology

Hematology samples will be collected as described in [Table 7-1](#) and [Table 7-2](#), following local standard practice.

Safety laboratory parameters monitored during the study will include hematocrit, hemoglobin, MCH, MCHC, MCV, platelets, red blood cells, white blood cells (WBC) count with differential (basophils, eosinophils, lymphocytes, monocytes, neutrophils), RBC Morphology

7.2.2.6.2 Clinical chemistry

Clinical chemistry samples will be collected as described in [Table 7-1](#) and [Table 7-2](#) following local standard practice.

Parameters to be measured will include: albumin, alkaline phosphatase, ALT (SGPT), AST (SGOT), bicarbonate, calcium, chloride, serum creatinine, creatine kinase, glucose, inorganic phosphorus, potassium, sodium, total bilirubin (direct and indirect bilirubin only required if total bilirubin is > 1.5 ULN) total cholesterol, LDL, HDL, lactate dehydrogenase (LDH), total protein, triglycerides, blood urea nitrogen (BUN) or urea, uric acid, C-reactive protein (CRP).

In addition, serum creatinine will be measured every 2 weeks during the first four weeks after first study drug administration and then monthly. Refer to [Table 7-1](#) and [Table 7-2](#) for specifics.

Creatinine clearance will be estimated using the Cockcroft-Gault equation for adult patients and Schwartz formula for pediatric patients. This estimate will be provided each time serum creatinine is collected. The formula should be consistently used throughout the study for a particular patient.

Use the following reference source for calculation of creatinine clearance:

- <https://reference.medscape.com/calculator/creatinine-clearance-cockcroft-gault>
- <http://wwwusers.med.cornell.edu/~spon/picu/calc/crclsch2.htm>

Serum ferritin test will also be performed at the screening visit to assess the eligibility of the patient. Serum ferritin testing will also be performed as described on [Table 7-1](#) and [Table 7-2](#).

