7.1 Study flow and visit schedule

Table 7-1 and Table 7-2 list all of the assessments and indicate with an “X”, the visits when they are performed. All data obtained from these assessments must be supported in the patient’s source documentation.

No CRF will be used as a source document.

Patients should be seen for all visits to perform the scheduled assessments on the designated day, or as close to it as possible, i.e., not exceeding ± 2 days for all assessments scheduled in Visits 1 to 7 and ± 7 days for all other visits till Visit 26. Study visits must be anchored (calculated) based on the baseline visit.

All Baseline assessments indicated in Table 7-1 and Table 7-2 must be completed prior to initiating Deferasirox DT treatment.

Study evaluation completion (SEC / Visit 777) should be performed as follows:

- For discontinuers or completers of the core phase, who do not roll over to the extension phase, SEC has to done within 7 days of discontinuing treatment.
- For completers of the extension phase, the SEC needs to be performed after receiving 96 weeks of treatment. The Study Evaluation Completion (777) and W96 visit will occur on the same visit and same date.

In this clinical trial, a week is 7 calendar days.

All data obtained from these assessments must be supported in the patient’s source documentation. The table indicates which data are entered into the database (D) or remain in source documents only (S) (column category).

Table 7-1 Visit Evaluation Schedule - Core Phase

Visit Number	Category	Protocol Section 7.2	Screening	Baseline	CORE PHASE treatment ⁴												
					1	2 ¹²	3	4	5	6	7	8	9	10	11	12	13
Study Week			Up to 28days prior to Baseline	D1	W2	W4 (M1)	W8 (M2)	W12 (M3)	W16 (M4)	W20 (M5)	W24 (M6)	W28(M7)	W32 (M8)	W36 (M9)	W40 (M10)	W44 (M11)	W48 (M12)
Informed consent	(D)	7.1.1	X														
Inclusion/ exclusion criteria	(D)	7.1.1.1	X	X													
History of disease	(D)	7.1.1.3	X														
Demography ¹³	(D)	7.1.1.3	X														
Relevant medical history/current medical conditions	(D)	7.1.1.3	X														
Prior chelation therapy ¹	(D)	7.1.1.3	X														
Transfusion/RBC History	(D)	7.1.1.3	X														X
Transfusions received	(D)	7.1.2	X	X	X	X	X	X	X	X	X	X	X	X	X	X	X
Physical exam	(S)	7.2.2.1	X	X	X	X	X	X	X	X	X	X	X	X	X	X	X
Weight	(D)	7.2.2.3	X	X	X	X	X	X	X	X	X	X	X	X	X	X	X
Height	(D)	7.2.2.3	X														X
Vital signs	(D)	7.2.2.2	X	X	X	X	X	X	X	X	X	X	X	X	X	X	X
Ocular exam	(D)	7.2.2.5	X														X

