⁴ The study will last until one of the patient withdrawal criteria is met ([Section 7.1.3.1](#)). At that time, the patient needs to complete the Study Evaluation Completion (SEC / 777) visit, and then FUP visit 30 days after last dose of study drug.

⁵ Last dose of deferasirox DT will be dispensed on Week 24, and taken by the patient until Week 24 day 7. At the Week 24 visit, the site will also dispense deferasirox FCT. The patient will take the first dose on Week 25 day 1.

⁶ Week 48 Visit (visit number 15) is a combined visit as it is the last visit of the Core Phase and the Baseline visit for the extension phase

⁷ If the patient switches treatment, the investigator must provide the preference questionnaire to the patient in the immediate next visit. Please refer to [Appendix 14.3](#) for further information.

⁸ "PROs" include observer reports for patients 2-9 years old

⁹ Palatability, satisfaction and GI symptoms questionnaires will be provided to the patient on Screening (visit number 1), during the 5 days of wash-out period from previous iron chelators therapies

¹⁰ Completion of PRO questionnaires at screening visit for ICT naïve patient or patients who did not take any ICT treatment within the 6 months prior to screening is not required

[figure not shown]
¹¹ Completion of palatability questionnaires at screening visit for patients who received Deferoxamine as prior chelation therapy is not required

¹² All Baseline assessments indicated in [Table 7-1](#) and [Table 7-2](#) must be completed prior to initiating Deferasirox DT treatment.

¹³ The investigators will have to re-assess, every 6 months, the childbearing potential of female patients aged 13 and older who are pre-menarche at the time of enrolling in the study. Once patient is able to bear children, they will need to undergo a urine pregnancy test in the next consecutive visit and then follow the VES for the urine and serum pregnancy tests.

Table 7-2 Visit Evaluation Schedule - Extension Phase

	Category	Protocol Section 7.2	Baseline EXT	EXTENSION PHASE treatment ⁴											Study Evaluation Completion ²	Safety Follow up
Visit Number			15 ⁵	16	17	18	19	20	21	22	23	24	25	26	777	501
Study Week			W48 (M12)	W52 (M13)	W56 (M14)	W60 (M15)	W64 (M16)	W68 (M17)	W72 (M18)	W76 (M19)	W80 (M20)	W84 (M21)	W88 (M22)	W92 (M23)	W96 (M24)	30 days after last dose of study drug received
Informed consent	(D)	7.1.1														
Inclusion/exclusion criteria	(D)	7.1.1.1														

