## 5.3 Laboratory parameters derivations

**Table 5.3.1 Definition of notable/extended ranges for laboratory test**

| Laboratory test                          | Criteria for notable ranges  |
|--|--|
| Platelet count                           | < 100 x 10  /L (extended range <50×10  /L)   |
| Absolute neutrophils                     | < 1.5 x 10  /L (extended range <0.5×10  /L)  |
| Serum creatinine                         | > 33% increase from baseline and > ULN at two consecutive measurements at least 7 days apart   |
| Creatinine clearance*                    | <60 mL/min at two consecutive measurements at least 7 days apart (extended range <40 mL/min at two consecutive measurements at least 7 days apart) |
| Urinary protein/urinary creatinine ratio | ≥ 1.0 (mg/mg) at two consecutive measurements at least 7 days apart  |
| ALT and AST                              | >5 x ULN and >2 x baseline value (extended range >10×ULN and >2×baseline value)  |

\* Creatinine clearance will be estimated using the Schwartz formula

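### Schwartz clearance is due at every visit for children, but height is scheduled only at Screening and Week 48; with the last scheduled height, clearance is understated in a sawtooth that peaks at Weeks 44 and 96

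*Protocol*

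**What the plan says.** **Formula and frequency.** Protocol section 7.2.2.6.2: "Creatinine clearance will be estimated using the Cockcroft-Gault equation for adult patients and Schwartz formula for pediatric patients". It continues: "This estimate will be provided each time serum creatinine is collected". On timing, "serum creatinine will be measured every 2 weeks during the first four weeks after first study drug administration and then monthly". The creatinine and clearance rows of Tables 7-1 and 7-2 are marked at every visit from Screening to the Week 96/SEC visit.

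**Height.** Section 7.2.2.3 describes how height and weight are taken ("Height in centimeters (cm) and body weight (to the nearest 0.1 kilogram (kg) in indoor clothing") and leaves the timing to the two tables. In Table 7-1 the height row has two marks, Screening and Week 48. In Table 7-2 it has one, in the Week 48 column, and nothing from Week 52 to Week 96 or at the SEC visit. Weight is marked at every visit in both tables.

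**Week 48.** A footnote to Table 7-1 makes Visit 15 serve two purposes: it closes the core phase and opens the extension. The single height mark in Table 7-2 is therefore the same measurement as the last one in Table 7-1.

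**Use of clearance.** Protocol Table 10-1 and SAP Table 5.3.1 flag clearance below 60 mL/min (extended range below 40) on two consecutive measurements at least 7 days apart. The SAP footnote reads "Creatinine clearance will be estimated using the Schwartz formula". Protocol section 10.5.3.3 compares laboratory values between DT (Day 1 to Week 24) and FCT (Weeks 25 to 48). SAP section 2.8.3 takes the laboratory baseline at the start of each period.

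**The concern.** The Schwartz estimate is a constant times height divided by serum creatinine. The documents do not print it; this is the definition of the method they name. A child's clearance therefore needs a current height, and the schedule supplies one at only two visits. The adult formula has no such gap, because its changing body-size input, weight, is taken at every visit. The study enrols from age 2.

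At visits without a height, a site that keeps to the schedule has only the last one. In a growing child that height is too small, so clearance comes out too low. DT always precedes FCT, so height is on average older in the FCT period. The error is systematic: more patients do not average it out, and requiring two consecutive low values does not remove it.

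**Working it through.** The plan gives no figure to reproduce. The check has two parts: the age of the latest scheduled height at each visit, and the error this causes.

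**Inputs from the documents.** Visits at Day 1, Weeks 2, 4, 8 and then every 4 weeks to Week 96. Height at Screening (up to 28 days before Day 1) and at Week 48.

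**Assumptions.** Screening falls 4 weeks before Day 1, the maximum allowed. The last scheduled height is carried forward. Growth is linear. Heights and growth rates are illustrative.

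**Age of height (weeks).** Day 1: 4. Week 24: 28. Week 28: 32. Week 44: 48. Week 48: 0. Week 52: 4. Week 96: 48.

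**Formula.** Understatement = g·t / (H + g·t), where H is the last measured height in cm, g is growth in cm/year, and t is the age of that height in weeks divided by 52.18.

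Example, 87 cm and 8 cm/year, at Week 44: g·t = 8 × 48/52.18 = 7.36 cm, and 7.36/94.36 = 7.8%.

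| Height at Screening, growth | Wk 24 | Wk 44 | Wk 48 | Wk 52 | Wk 96 | Mean, DT visits (Wks 2–24) | Mean, Wks 28–48 |
|---|---|---|---|---|---|---|---|
| 85 cm, 8 cm/yr | 4.8% | 8.0% | 0 | 0.7% | 7.3% | 2.8% | 5.6% |
| 87 cm, 8 cm/yr | 4.7% | 7.8% | 0 | 0.6% | 7.2% | 2.8% | 5.5% |
| 110 cm, 6 cm/yr | 2.8% | 4.8% | 0 | 0.4% | 4.5% | 1.7% | 3.3% |
| 130 cm, 5 cm/yr | 2.0% | 3.4% | 0 | 0.3% | 3.3% | 1.2% | 2.4% |
| 160 cm, 1 cm/yr | 0.3% | 0.6% | 0 | <0.1% | 0.6% | 0.2% | 0.4% |

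**Flags.** Take the 87 cm child with a current-height clearance of 64 mL/min. At Week 40 the height is 44 weeks old and the understatement is 7.2%, so the value reads 64 × 0.928 = 59.4. At Week 44 it reads 64 × 0.922 = 59.0. Both fall below 60 and together meet the two-measurement rule. Across the table, a Week 44 reading of 60 corresponds to a current-height value between 60/0.994 = 60.4 and 60/0.920 = 65.2.

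**Change from period baseline.** Up to Week 44 the FCT baseline (Week 24) and the FCT visits share the same screening height, so only growth since baseline counts. Mean time since baseline is (4+8+12+16+20)/5 = 12.0 weeks for FCT, against (2+4+8+12+16+20+24)/7 = 12.3 weeks for DT. In the 87 cm child the mean artefact is about −2.0% in FCT and −2.1% in DT, so the two periods are balanced. At Week 48 height is renewed while the baseline stays 4.7% low: 1/(1 − 0.047) = 1.049, a spurious rise of about 5%. At Week 44 the same child showed 0.922/0.953 = 0.967, a spurious fall of about 3%.

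**The case against.** Several points on the other side stand.

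- **Carry-forward is not written down.** Neither document tells sites to reuse an old height or forbids measuring a child at the visit. The bias is therefore conditional. But if some sites measure and others do not, practice differs with no recorded rule, which also needs settling.
- **A reader might infer that understatement grows steadily through the FCT period and the extension.** The schedule does not support that. The drift begins under DT, and height is renewed at Week 48. At Week 52 the error is at most 0.7% in the table, less than the same child has at Week 24.
- **The period baseline balances much of the DT–FCT comparison.** This holds for change from baseline up to Week 44. It does not cover levels, the flags or the Week 48 step.
- **Growth is assumed.** Protocol section 1.1 names growth retardation as a complication of this disease and its iron overload, so slow growth is plausible and the upper figures may apply to few children. The documents give no paediatric share.
- **Consequences are limited.** A reader might infer that dose decisions or enrolment are compromised. The renal dose-reduction rule in section 6.2.1.2 rests on serum creatinine, and eligibility uses the height taken at Screening. The primary endpoint is preference.

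The footnote to SAP Table 5.3.1 (and Protocol Table 10-1) names Schwartz with no age limit, whereas section 7.2.2.6.2 confines it to children. That conflict is separate from this point, but the two should be reconciled when the height rule is written.

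**Conclusion.** The point holds as a flaw in the assessment schedule: a height-based estimate is required at every visit, and a current height is available at two of them. Under carry-forward the error is a downward sawtooth that never exceeds about one year's growth. It is about 0.6% to 8% at Week 44 over the assumed range and near zero in adolescents who have almost stopped growing. For the assumed 87 cm, 8 cm/year child the mean is 2.8% over the DT visits and 5.5% over Weeks 28–48.

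The affected outputs are paediatric clearance levels, the <60 and <40 mL/min flags, and the Week 48 change from the FCT-period baseline. Change from period baseline up to Week 44 is roughly balanced between formulations. These sizes rest on carry-forward, linear growth, a 4-week screening interval and illustrative growth rates; the gap in the schedule rests on none of them. The point is worth correcting because paediatric renal values are a planned safety output, but it does not threaten the primary analysis.

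**What to change.** **Schedule.** In Tables 7-1 and 7-2, add height for patients under 18 at existing visits: every visit with a clearance estimate or, at the least, every 12 weeks, plus Week 96 and the SEC visit. Measuring at every such visit removes the error. Every 12 weeks limits it to about 2% in the fastest-growing case (8 × 12/52.18 = 1.84 cm on 85 cm; 1.84/86.84 = 2.1%).

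**SAP.** State that the height current at the visit enters the paediatric formula.

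**Core data already collected.** Recompute clearance for analysis with height interpolated linearly between Screening and Week 48. Add a stated rule for patients who leave before Week 48, since the SEC visit has no height. Interpolation cannot correct the value a site calculated on the day, and it does not reach the extension, where no second height exists.

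**Cost.** Height is a database item, so the schedule change needs a minor amendment and eCRF update, plus about a minute per child per visit. At Amendment 1, 132 patients were already enrolled, so added heights would help mainly visits still to come. Interpolation costs SAP text and programming only.
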